## 9.0 SEQUENCE OF PLANNED ANALYSES

### Final analysis of safety and efficacy at the primary short-term endpoint ( [REDACTED] following last subject dosed)

An interim analysis will be performed using data from all subjects with a [REDACTED] assessment.

### Long-term follow-up analysis of safety and efficacy (5 years post-last OpRegen dose)

Final analysis will be performed using data from all subjects with a Year 5 post-treatment assessment.

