All SAEs (DLTs refer to section 10.2) will be carefully monitored throughout the course of the study. Collection of SAE information will begin upon the subject's signing of the informed consent through the end of the long-term follow-up period, or for as long as is necessary per the Investigator's discretion (whichever is later). SAEs may be either spontaneously reported or elicited during questioning and examination of the subject. All identified SAEs must be recorded and described in the subject's source records. If known, the diagnosis of the underlying illness or disorder should be recorded, rather than its individual symptoms. All SAEs will be classified as related or not related to the study drug. All SAEs must be reported to the Sponsor as soon as possible and no later than 24 hours after the Investigator has knowledge of the event. Serious adverse events will be reported by completing the SAE form provided by the Sponsor. Refer to the Safety Management Plan for procedures and reporting requirements.

If a subject terminates study participation early after receiving any amount of study drug/SAEs will be collected for at least 12 weeks after the last dose

of per protocol drug, regardless of the investigator's opinion of causation. Thereafter, SAEs are not required to be reported unless the investigator feels the events were related to either study drug/per protocol medication, or a protocol procedure.

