22.2 ANALYSIS SETS

22.2.1 Modified Intent-to-Treat (mITT) Analysis Set

The Modified Intent-to-Treat (mITT) analysis set will consist of all subjects who have been enrolled to the trial and received the OpRegen® implantation. This analysis set, which will include all data captured in database for these subjects, will serve as the primary Analysis Set for inference.

22.2.2 **Per Protocol (PP) Analysis Set**

The Per Protocol (PP) analysis set is a subset of the mITT Analysis Set and will consist of all subjects who have been enrolled into the trial, received the OpRegen® implantation and violated none of the major protocol guidelines.

22.3 **SIGNIFICANCE LEVEL**

No formal hypothesis testing is planned for this study. However, a significance level of 0.05 using two-tailed tests will be utilized in the case that exploratory significance testing will be performed.

22.4 **INTERIM REPORTS**

Comprehensive interim reports of accumulated safety, tolerability and preliminary available efficacy data will be presented to the independent Data Safety Monitoring Board (DSMB).

Depending on the safety data available, there will be a DSMB recommendation to pursue one of the following alternatives: proceed to the next higher dose; stop dose escalation; investigate a lower dose; or repeat a dose level.

22.5 **DESCRIPTIVE STATISTICS**

All measured variables and derived parameters will be listed individually and if appropriate, presented in summary tables by dose regimen group and overall, providing sample size, absolute and relative frequency for categorical variables, or sample size, arithmetic mean, standard deviation, median, minimum and maximum for continuous variables. Confidence intervals will be presented for the efficacy endpoints for exploratory purposes only.

22.6 **MISSING DATA**

Every effort will be made to complete follow-up for all subjects and avoid missing data, in particular regarding essential items. For other cases of missing data, the “last observed value” (LOV) approach will be used when appropriate.

22.7 **SUBJECT DISPOSITION**

Data from subjects who are screened but not treated, subjects in the mITT and PP Analysis Sets, as well as trial withdrawals from study follow-up will be summarized using descriptive statistics.

22.8 **DEMOGRAPHIC AND BASELINE CHARACTERISTICS**

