### 6.1 Analysis Sets

#### All Treated Population

The All Treated Population will include all subjects who received OpRegen. This will be used for all safety and efficacy analyses.

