### 7.1.6 Adverse Events

The collection period for adverse events for the purposes of this protocol begins once the subject has signed the informed consent form and ends after the [REDACTED]. All adverse events will be listed by subject. The [MedDRA](#) (Version 25.0) will be used to classify all adverse events by SOC and PT.

A treatment emergent adverse event ([TEAE](#)) will be considered as any [AE](#) that starts on or after the date and time of the OpRegen administration, or if an [AE](#) that started before the OpRegen injection worsened after the administration of the investigational product.

A topline summary of treatment emergent adverse events with the number of events, number of subjects, and percentage of subjects for each category below will be tabulated by cohort.

- Any [TEAE](#) and [SAE](#)
- Subjects reporting at least one [TEAE](#) or [TE SAE](#) that is also related to OpRegen
- [TEAE](#) and [SAE](#) Severity: Grade 1/Mild, Grade 2/Moderate, Grade 3/Severe, Grade 4/Life Threatening/Disabling, Grade 5/Fatal
- Categories for all [TEAE](#) and with possible relationship to OpRegen

The following tables will be presented for the number of events by cohort:

- [TEAE](#) by preferred term sorted by descending number of overall events
- [TEAE](#) by SOC, PT\*
- [TEAE](#) by maximum severity\*
- [TEAE](#) by Possible Relationship to OpRegen\*

\*Subjects with >1 [AE](#) in respective category will only be counted once. For maximum severity tabulations, subjects will be counted once in the SOC and PT in the maximum severity.

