### **Statistical summary conventions**

For tables, sample sizes for each treatment group will be presented as totals in the column header (N=x), where appropriate. Sample sizes shown with summary statistics are the number (n) of subjects with non-missing values.

Summaries for categorical variables will include only categories that subjects had a response in. Percentages corresponding to null categories (cells) will be suppressed. All summaries for continuous variables will include: N, mean, and SD. Other summaries (e.g. median, quartiles, 5%, 95% intervals, CV or %CV) will be used as appropriate. All percentages should be rounded and reported to a single decimal place (xx.x%). If percentages are reported as integers, percentages greater than 0% but <1% will be reported as <1%, whereas percentages greater than 99% but <100% will be reported as >99%. A percentage of 100% will be reported as 100%. No value of 0% should be reported. Any computation of percent that results in 0% is to be reported as a blank. P-values will be reported with three decimal places with a leading zero (0.001). P-values <0.001 will be reported as <0.001.

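### SAP 9.0 selects the long-term safety and efficacy data by having a Year 5 assessment, which conflicts with the All Treated rule in SAP 6.1; read literally, every death before Year 5 is tabulated as none

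*SAP*

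**What the plan says.** SAP 9.0 has two paragraphs, each headed as an analysis of safety and efficacy. The long-term one reads: "Final analysis will be performed using data from all subjects with a Year 5 post-treatment assessment". The short-term one is built the same way: "An interim analysis will be performed using data from all subjects with a [REDACTED] assessment". Neither refers to an analysis set, and neither exempts the safety summaries.

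SAP 6.1 sets a different rule: "The All Treated Population will include all subjects who received OpRegen. This will be used for all safety and efficacy analyses". Protocol 22.2.1 agrees with 6.1. Its primary set is every enrolled and implanted subject, and "This analysis set, which will include all data captured in database for these subjects, will serve as the primary Analysis Set for inference".

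Four other provisions bear on the point:

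- Protocol 12 lists adverse events and death among the reasons for leaving the study.
- Protocol 21.1.2 collects serious adverse events from "signing of the informed consent through the end of the long-term follow-up period", with a narrower rule for subjects who terminate early.
- SAP 7.1.6 tabulates severity up to "Grade 4/Life Threatening/Disabling, Grade 5/Fatal" and names no analysis set for those tables.
- SAP 10.0 adds two printing rules: "Summaries for categorical variables will include only categories that subjects had a response in" and "Any computation of percent that results in 0% is to be reported as a blank".

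On withdrawal, Protocol 22.11 plans Kaplan-Meier curves of time to AE-related withdrawal and of overall discontinuation, repeated for Part 2. The SAP methods and figure list contain no such curves. SAP 7.1.1 follows disposition only to the 1 Year Visit. SAP 11.0 lists a Time in Study table (14.1.2) and an Early Discontinuations table (14.1.3), neither with a stated time limit.

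**The concern.** Safety and tolerability are the primary objective. A rule that admits only subjects seen at Year 5 selects on survival and retention, which are themselves safety and tolerability outcomes. A subject who dies before Year 5 cannot have that assessment, so the fatal row would contain no death before Year 5, whatever happened. Under the SAP 10.0 conventions the row would then be left out or printed blank, not shown as zero.

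For other events the tabulated rate could move either way, depending on whether the subjects who left had the event. It would be too low when events lead to withdrawal.

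The choice between 6.1 and 9.0 is left to whoever programs the tables, and it sets the denominator of every long-term safety percentage.

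**Working it through.** **1. The plan's own figure.** SAP 4.0 gives cohorts of 3, 3, 6 and 12: 3 + 3 + 6 + 12 = 24, which matches the 24 treated eyes in SAP 6.0. There is no power calculation, attrition allowance or expected event rate to reproduce.

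**2. The two rules side by side.**

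| Subject | SAP 6.1 / Protocol 22.2.1 | SAP 9.0, literal |
|---|---|---|
| Treated, seen at Year 5 | in | in |
| Treated, died before Year 5 | in | out |
| Treated, withdrew before Year 5 | in | out |

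The rules agree only if all 24 reach Year 5.

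**3. Size of the long-term set.** The annual loss r is assumed. Number lost k = 24 × (1 − (1 − r)^5):

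- r = 2%: 2.31, so k = 2 and N = 22
- r = 5%: 5.43, so k = 5 and N = 19
- r = 10%: 9.83, so k = 10 and N = 14

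**4. Deaths.** Two deaths before Year 5 (assumed) are 2/24 = 8.3% of all treated. In the literal set they are 0/22, 0/19 or 0/14.

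**5. Other events.** With x event subjects among 24, the literal rate lies between max(0, x − k)/(24 − k) and min(x, 24 − k)/(24 − k). Here x is assumed.

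| | All treated | k = 2, N = 22 | k = 5, N = 19 | k = 10, N = 14 |
|---|---|---|---|---|
| x = 2 | 8.3% | 0% to 9.1% | 0% to 10.5% | 0% to 14.3% |
| x = 6 | 25.0% | 18.2% to 27.3% | 5.3% to 31.6% | 0% to 42.9% |

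These are arithmetic extremes, not predictions. If loss were unrelated to the event, the chance that at least one of two event subjects drops out is 1 − (24 − k)(23 − k)/(24 × 23): 16.3%, 38.0% or 67.0%.

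**6. Precision when no event is seen.** The one-sided 95% upper limit is 1 − 0.05^(1/N): 11.7% at N = 24, then 12.7%, 14.6% and 19.3% at N = 22, 19 and 14.

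**7. Efficacy.** SAP 6.3 imputes only dates. A Year 5 mean therefore uses the subjects with a Year 5 value under either rule, and the two means are identical. At an earlier visit where all 24 were seen, mean(all) − mean(stayers) = (k/24) × (mean(leavers) − mean(stayers)). That is 8.3%, 20.8% or 41.7% of the leaver-stayer difference, in a direction the documents do not give.

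**8. The all-treated benchmark.** After early termination, Protocol 21.1.2 requires serious events to be collected for at least 12 weeks after the last per-protocol drug. Beyond that, only events the investigator considers related to study drug, per-protocol medication or a protocol procedure are required. So x/24 counts every recorded event but is not a fully observed five-year rate.

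**The case against.** The strongest reply is that 9.0 concerns timing. Its title is about the sequence of analyses. Analysis sets are defined in 6.1, which is explicit. No Year 5 completer set is defined anywhere, and every output title must name its population. The literal reading would also leave little or nothing for the Early Discontinuations table in a Year 5 run. The drafting of 9.0 is loose in any case: the short-term paragraph is headed as a final analysis, while its text calls it interim.

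This stands as a plausible account of intent. It does not settle the text, because the headings already give the timing and the sentences beneath them then say whose data are used. A reader might infer that the SAP definitely plans to exclude early deaths. The documents do not support that; they support only two rules left unreconciled.

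Other stronger readings also fail:

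- *The events would vanish from the report.* They would not. SAP 7.1.6 lists all adverse events by subject, SAP 11.0 has a listing of fatal outcomes, and the column N and population title would show a smaller set. These reveal the exclusion but do not correct the tabulated rates.
- *The short-term analysis is affected in the same way.* This cannot be established. Its time point is redacted, and the end-of-Part-1 visit in the protocol also serves as the early-discontinuation visit, so some early leavers may count as assessed.
- *Withdrawal during Part 2 is not described at all.* Tables 14.1.2 and 14.1.3 carry no one-year limit. What is missing is the Kaplan-Meier analysis and a disposition summary beyond Year 1.

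The printing rules apply whatever 9.0 means. They make an exclusion harder to notice but do not cause it.

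**Conclusion.** The conflict between SAP 9.0 and SAP 6.1 (with Protocol 22.2.1) is in the current text and should be fixed; confidence is medium. On the literal reading, deaths before Year 5 are always tabulated as none in the long-term safety tables, and other event rates can shift in either direction. The sizes shown rest wholly on assumed losses of 2% to 10% a year and assumed event counts. If no one is lost before Year 5, the difference is zero.

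The Year 5 efficacy mean is unaffected as long as the no-imputation rule of SAP 6.3 is followed; only earlier-visit efficacy summaries within the long-term analysis could move.

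The Kaplan-Meier omission is a separate difference between protocol and SAP. Protocol 22.1 allows the SAP to modify the protocol's plans, but the SAP does not present this as a change.

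**What to change.** Reword both paragraphs of SAP 9.0 as timing rules, for example: *The analysis is performed once the last subject has completed the visit or left the study, using all data from the All Treated Population.* Label any summary restricted to subjects with the landmark visit as supportive. If a data-cut rule was meant, this only confirms it.

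Separately:

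- Restore the Protocol 22.11 Kaplan-Meier curves for AE-related and overall withdrawal in Parts 1 and 2, or state in the SAP that they are dropped and why.
- Extend the disposition items in SAP 7.1.1 through Year 5.
- In SAP 7.1.10, replace the undefined Intent to Treat label with All Treated Population. This is a minor label correction.

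The core change costs two sentences. The additions need one longer table and a few figures, built from last study day and total days on study, which SAP 4.1.1 already derives. No new data are needed. SAP 2.0 requires revisions before database lock, so the wording should be settled by then.

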## 10.0 REPORTING CONVENTIONS

### General reporting conventions

All tables, listing and figures (TLFs) will be presented in portrait orientation, unless landscape orientation suggests that the information is easier to view. Legends will be used for all figures with more than one variable or item displayed. Figure lines should be wide enough to see the line after being copied.

All TLFs will have the name of the relevant SAS program (output name), the author, and a date-time stamp on the bottom of each output. All outputs will be produced on PDF to avoid changes during medical writing processes.

Titles should contain the following information:

- Output number
- Description of the data that is being summarized
- Type of analysis performed, and covariates used (if applicable)
- Analysis population

### **Statistical summary conventions**

For tables, sample sizes for each treatment group will be presented as totals in the column header (N=x), where appropriate. Sample sizes shown with summary statistics are the number (n) of subjects with non-missing values.

Summaries for categorical variables will include only categories that subjects had a response in. Percentages corresponding to null categories (cells) will be suppressed. All summaries for continuous variables will include: N, mean, and SD. Other summaries (e.g. median, quartiles, 5%, 95% intervals, CV or %CV) will be used as appropriate. All percentages should be rounded and reported to a single decimal place (xx.x%). If percentages are reported as integers, percentages greater than 0% but <1% will be reported as <1%, whereas percentages greater than 99% but <100% will be reported as >99%. A percentage of 100% will be reported as 100%. No value of 0% should be reported. Any computation of percent that results in 0% is to be reported as a blank. P-values will be reported with three decimal places with a leading zero (0.001). P-values <0.001 will be reported as <0.001.

## 11.0 SUMMARY TABLES, FIGURES AND DATA LISTINGS

### List of Tables

Table Number	Table Title
14.1.1	Subjects Disposition
14.1.2	Time in Study
14.1.3	Early Discontinuations
14.1.4.1	Demography screened subjects
14.1.4.2	Demography
14.1.6	Physical Examination
14.1.7	General Medical History
14.1.8	Concomitant Medications
14.1.9	Per Protocol Medications
14.1.10	AMD History
14.1.11	Ocular History
14.1.5	OpRegen Surgical Procedure
14.3.1.1.1	Frequency and Incidence of Treatment Emergent Adverse Events by MedDRA System Organ Class
14.3.1.1.2	Frequency and Incidence of Treatment Emergent Adverse Events by MedDRA System Organ Class and Preferred Term
14.3.1.2.2	Frequency and Incidence of Serious Treatment Emergent Adverse Events by MedDRA System Organ Class, Preferred Term
14.3.1.4.2	Frequency and Incidence of Treatment Emergent Adverse Events by Event Relationship to Per Protocol Treatment MedDRA System Organ Class, Preferred Term
14.3.1.8.2	Frequency and Incidence of Treatment Emergent Adverse Events by Ocular Toxicity MedDRA System Organ Class, Preferred Term
14.3.1.9.2	Frequency and Incidence of Treatment Emergent Adverse Events by Systemic Toxicity MedDRA System Organ Class, Preferred Term
14.3.3.2	Vital Signs
14.3.2	Laboratory results
14.2.1	Efficacy Geographic Atrophy
14.2.2	Efficacy Best Corrected Visual Acuity
14.2.3.1	Efficacy Intra-Ocular Pressure

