7.3 STUDY ENDPOINTS

7.3.1 Safety and Tolerability Endpoints

Safety and tolerability of OpRegen treatment will be assessed by:

- Incidence and frequency of treatment emergent AEs
- Treatment emergent changes in the following variables:
 - Vital signs
 - Hematology/ Blood Chemistry/Urinalysis
 - Physical examination

- Ophthalmological evaluations including:
 - ✓ BCVA
 - ✓ Dilated Fundus Exam
 - ✓ IOP
 - ✓ SLE
 - ✓ SD-OCT
 - ✓ FA
 - ✓ Microperimetry
 - ✓ FAF
 - ✓ CFP

[REDACTED]

[REDACTED]

[REDACTED]

[REDACTED]

[REDACTED]

- [REDACTED]
- [REDACTED]
- [REDACTED]

[REDACTED]

- [REDACTED]

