### 3.2 Study Endpoints

#### 3.2.1 Safety and Tolerability Endpoints

Safety and tolerability of OpRegen treatment will be assessed by:

- Incidence and frequency of treatment emergent adverse events ([AEs](#))
- Treatment emergent changes in the following variable:
  - Ophthalmological evaluation:
    - ✓ Intraocular Pressure ([IOP](#))

[REDACTED]

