## 6.2 Significance Level

Though no formal hypothesis testing was originally planned for this study, for purposes of this SAP, a significance level of 0.05 using two-tailed tests will be utilized for any exploratory significance testing performed.

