## 6.3 Procedures for Handling Missing Data and Outliers

Missing or incomplete dates will be imputed per [Section 4.1.1](#) for the purposes of determining treatment emergence. All other missing data will not be imputed, unless otherwise noted.

All unscheduled visit data will be included in data listings. In the data summary tables, the presence of missing data will be indicated by the inclusion of a 'missing' category with categorical data, and a count and percentage of missing observations for continuous numeric data, where applicable.

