### 7.1.10 Efficacy Analyses

All efficacy data will be listed for all subjects. Efficacy summaries will be presented for the Intent to Treat Population for all variables.

- Directional change in the geographic atrophy ([GA](#)) lesion area over time
- Overall change in the [GA](#) lesion area of the study eye over time using [FAF](#)
- Change from baseline over time in [BCVA](#) as measured by Early Treatment Diabetic Retinopathy Study ([ETDRS](#)) chart
- Change from baseline over time in Low Luminance [BCVA](#)
- Change from baseline over time in [IOP](#)

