## 8.0 GENERAL CONSIDERATIONS

In general, numerical variables in demographic and baseline characteristics will be summarized by displaying: n (non-missing sample size), mean, standard deviation, median, quartiles, maximum and minimum. The frequency and percentages (based on the non-missing sample size) of observed

levels will be reported for all categorical measures. Percentages will be calculated out of the total number of subjects per group.

Numerical effectiveness variables described above will be summarized displaying n, mean, median, standard deviation ([SD](#)), standard error (SE), quartiles, minimum, maximum.

All summary tables will be structured with a column for either treated or fellow eye.

No inferential statistics will be applied to baseline characteristics and safety variables unless specified otherwise.

In general, all data will be listed and sorted by treatment or fellow eye status, cohort number, site and subject, and when appropriate by visit number (or assessment date) as appropriate.

Most data manipulation, tables, figures, listings, and analysis will be documented in SAS programs and performed using SAS® Software version 9.4.

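### The SAP defines IOP as a safety endpoint but reports it only as an efficacy change from baseline, with no count of eyes above a pressure limit

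*SAP*

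**What the plan says.** **Defined as safety.** Protocol 7.3.1 gives nine eye assessments under "Ophthalmological evaluations including", IOP among them. SAP 3.2.1 shortens this to "Treatment emergent changes in the following variable" and names IOP alone. SAP Table 1 still marks other eye assessments as safety, such as the dilated fundus examination, fluorescein angiography and slit lamp. IOP is not in the SAP's own efficacy endpoint list (3.2.4).

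**Reported as efficacy.** SAP 7.1.10 lists IOP change from baseline among the efficacy analyses. Table 14.2.3.1, Figure 14.2.3 and Listing 16.2.3 are all titled "Efficacy Intra-Ocular Pressure". None of the 14.3 safety tables is for IOP.

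**Rules that depend on the label.** SAP 6.4 plans exploratory confidence intervals for efficacy endpoints. SAP 6.2 says that "a significance level of 0.05 using two-tailed tests will be utilized for any exploratory significance testing performed". SAP 8.0 says "No inferential statistics will be applied to baseline characteristics and safety variables unless specified otherwise".

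**What the IOP summary contains.** SAP 8.0 gives n, mean, median, SD, SE, quartiles, minimum and maximum, with treated and fellow eyes shown separately. SAP 7.1.10 lists every value. On readings outside the schedule, SAP 6.3 says "All unscheduled visit data will be included in data listings", and does not say whether they enter a summary table.

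**The concern.** Safety is the primary objective, and the SAP gives its one listed ophthalmic safety variable no output among the safety tables. The efficacy label raises two questions that the SAP does not answer: does IOP get the efficacy confidence intervals, and does the bar on inference for safety variables protect it from an exploratory test?

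The summary also suits the question poorly. Pressure harm after subretinal surgery would be expected in a few eyes with large rises, not as a shift in all eyes. A small mean change with a wide interval could be read as reassurance while one to four eyes had large rises. The protocol plans incidence tables of potentially clinically significant values for laboratory tests (22.10.2) and vital signs (22.10.3). Neither document plans the equivalent for IOP.

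**Working it through.** **Inputs from the documents.** SAP 4.0 gives 24 treated eyes: 3 + 3 + 6 + 12 = 24, which reproduces. SAP 6.2 gives two-sided 0.05 for any exploratory test. There is no power calculation to reproduce.

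**Inputs assumed.** The documents give no SD for IOP change and no pressure limit. I take unaffected eyes to change with mean 0 and SD s = 2 to 4 mmHg, and affected eyes to rise by d = 10 to 25 mmHg.

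**Why the mean hides a few eyes.** With k of n eyes raised by d:

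- mean change = k·d/n
- SD² = s² + d²·k(n − k)/[n(n − 1)]
- t = mean/(SD/√n)

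The same rises that move the mean also inflate the SD. For n = 24, d = 20, s = 3, k = 2: mean = 40/24 = 1.67; SD² = 9 + 400 × 44/552 = 40.88, so SD = 6.39; t = 1.67/(6.39/4.90) = 1.28, p = 0.21.

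**Hypothetical one-sample t test, 24 eyes.** Missed means p ≥ 0.05, from 20,000 simulated trials per scenario.

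| Eyes affected | Mean (d = 20) | SD (s = 3) | p from formula | Missed, s = 3, d = 20 | Missed, s = 2–4, d = 10–25 |
|---|---|---|---|---|---|
| 1 | 0.83 | 5.07 | 0.43 | 98% | 95–100% |
| 2 | 1.67 | 6.39 | 0.21 | 94% | 91–99% |
| 3 | 2.50 | 7.39 | 0.11 | 82% | 82–89% |
| 4 | 3.33 | 8.18 | 0.058 | 57% | 44–77% |
| 5 | 4.17 | 8.82 | 0.030 | 25% | 5–64% |
| 6 | 5.00 | 9.34 | 0.015 | 5% | 0–50% |

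With no affected eye, p ≥ 0.05 occurs in about 95% of trials, so one or two affected eyes give almost the same result as none. In Cohort 4 alone (n = 12, s = 3, d = 20) the miss rates for 1 to 5 affected eyes are 99%, 97%, 84%, 44% and 7%.

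**What a count would show (exact 95% CI).**

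- 1/24 = 4.2% (0.1–21.1%)
- 2/24 = 8.3% (1.0–27.0%)
- 3/24 = 12.5% (2.7–32.4%)
- 0/24: two-sided upper bound 1 − 0.025^(1/24) = 14.2%

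The chance of seeing at least one such eye in 24 is 1 − 0.95^24 = 71% at a true rate of 5%, and 1 − 0.90^24 = 92% at 10%.

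**Does the adverse-event route already count these eyes?** Protocol Table 6 grades glaucoma by the intervention needed and, at Grade 4, by blindness. It has no mmHg limit, and its lowest grade already requires topical treatment. Protocol 14.1 says that observed changes will be reported as adverse events. Protocol 21.1 makes an abnormal diagnostic result an adverse event only under listed conditions, one of them the investigator's view of clinical significance. A rise that was neither treated nor judged significant can therefore be absent from Table 14.3.1.8.2.

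**The case against.** The strongest reply is that this is a filing error with little consequence.

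- **No test is planned.** SAP 3.3 says no formal testing was planned, and SAP 6.2 applies only if an exploratory test is done. IOP is a safety variable by definition in 3.2.1 and is missing from the efficacy list in 3.2.4, so the natural reading is that the 8.0 bar covers it. This stands. A reader might infer that the SAP will test IOP and report no significant change; the documents do not say so. The miss rates above describe what could happen if it were tested.
- **Pressure events are already tabulated.** Table 14.3.1.8.2 gives adverse events by ocular toxicity, and raised pressure is graded there from the point at which it warrants topical treatment. Adverse events are also recorded at unscheduled visits (Protocol 13), and Grade 3–4 ocular toxicity feeds the stopping rules (Protocol 10.2). This largely stands. It would be wrong to say that no table counts raised pressure, or that sight-threatening rises would go unreported. The gap is limited to measured rises that were neither treated nor reported as events.
- **The summary is more than a mean.** Minimum, maximum, quartiles, a figure and a full listing are planned, and with 24 subjects a careful reader can find every eye. That is true, but the reader must do the counting, without a limit fixed in advance.
- **The calculation depends on assumptions.** It does, and the blind spot closes as more eyes are affected: with a 20 mmHg rise and SD 3, five affected eyes are missed only 25% of the time.

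**Conclusion.** The point holds in a limited form. IOP is defined as safety and reported only as efficacy, and no output counts eyes above a pressure limit. The label creates an ambiguity about intervals and inference; it does not commit the sponsor to a test.

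A summary built on mean change is weak where the number of affected eyes is small. Under the assumed SD of 2 to 4 mmHg and rises of 10 to 25 mmHg, a 0.05 test would miss 2 of 24 affected eyes in 91–99% of trials and 3 of 24 in 82–89%. It would usually not miss five or more eyes at 20 mmHg with SD 3. These figures rest on values that the documents do not supply.

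It would also go too far to say that IOP is the only ophthalmic safety variable the SAP keeps. That is true of the 3.2.1 list, but not of SAP Table 1. Relabelling alone would be close to clerical. Together with a count of eyes, it is a cheap and worthwhile improvement to the primary (safety) analysis.

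**What to change.** 1. Remove IOP from SAP 7.1.10 and move its table, figure and listing to the safety outputs (14.3 and 16.3), retitled.
2. State in SAP 8.0 that the bar on inference covers IOP.
3. Add one table with the number of eyes that exceed sponsor-set reporting limits, for rise from baseline and for absolute value, at any post-implantation visit, scheduled or unscheduled. Show it by cohort and overall, treated versus fellow eye, with exact 95% confidence intervals.
4. Cross-refer to Table 14.3.1.8.2 for treated events, and keep mean change as description.

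The limits should be fixed before database lock. They serve reporting only and set no clinical rule. IOP is already measured in each eye (SAP Table 1), so no new data are needed. The cost is SAP wording and one extra table, whose intervals will be wide: even 0/24 leaves a two-sided upper bound of 14.2%. That width also guards against reading an absence of events as proof of pressure safety.
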